Study Title:

Brain State-dependent Stimulation to Improve Movement (BrainSTIM)

NCT Number:

NCT05103176

Document:

Study Protocol and Statistical Analysis Plan

Document Date:

2/1/22

IRB STUDY TITLE:

Multi-Session investigations of State-dependent brain network manipulation.

ClinicalTrials.gov BRIEF TITLE:

Brain State-dependent Stimulation to Improve Movement (BrainSTIM)

GRANT/ClinicalTrials.gov OFFICIAL STUDY TITLE:

Leveraging behavioral state to enhance specificity of non-invasive brain stimulation on motor circuits

Who is eligible: Healthy, right-handed, English-speaking adults between the ages of 18 and 50 years with no history of neurological disorder

This study involves: Basic neurological assessments during a maximum of 9 visits

Compensation: up to \$270

SUBJECTS and SCREENING:

- To ensure experimental rigor, all research staff will be trained in Good Laboratory Practices, including standardized operating procedures and record keeping.
- We will recruit ~65 subjects (50% women), ages 18-50, to allow for drop-outs and subjects who cannot tolerate NIBS.
- All subjects should be in good health with normal or corrected-to-normal visual acuity, without any known contraindications to NIBS (“pre-screening” and “enrollment screening”).
- Subjects will be screened prior to enrollment, at time of enrollment and prior to all subsequent sessions with questions that include the Transcranial Magnetic Stimulation Adult Safety Screen form in order to exclude subjects with contraindications for TMS and MRI (Keel et al., 2001; Rossi et al., 2011) and adhere to published safety guidelines and recommendations (e.g. Rossini et al., 2015)
- Subjects will be screened for handedness with the Edinburgh handedness inventory (Oldfield, 1971).
- Prior to the start of the study, all participants will provide informed written consent in accordance with the Declaration of Helsinki.
- After consenting and prior to the start of the study, all participants will provide written attestation that they do not believe they are pregnant. Participants will be offered a self-administered urine pregnancy test, free of charge, upon request.

- For subsequent study sessions, all participants will complete a screening ("Daily screening") to confirm there are no changes in their eligibility.

Inclusion criteria:

1. Age 18-50
2. Right handed
3. English speaker
4. No history of neurological disorder
5. Able to provide written consent prior to admission

Exclusion criteria:

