Subjects and Screening: To ensure experimental rigor, all research staff will be trained in Good Laboratory Practices, including standardized operating procedures and record keeping. We will recruit ~65 healthy subjects (50% women), ages 18-50, to allow for drop-outs and subjects who cannot tolerate iTBS. Subjects will be screened with the Transcranial Magnetic Stimulation Adult Safety Screen^{5,6,7} form in order to exclude subjects with contraindications for TMS and MRI, such as: a previous adverse reaction to TMS, a history of seizures or a condition that would increase the likelihood for seizures, a family history of epilepsy, taking medications that would increase the risk of seizure, pregnant or trying to become pregnant, presence of metal in the head (other than in the mouth), claustrophobia, presence of an implanted device like a pacemaker, metal in the brain, or other brain injuries or brain-related conditions.

Initial Assessment Session (screening): Subjects will watch a demo video of the 9-hole pegboard dexterity test (9-HPT, described below) from the NIH Toolbox for Assessment of Neurological and Behavioral function⁸ (www.nihtoolbox.org) in order to standardize instructions and familiarize subjects with the task. Subjects then will practice on the 9-HPT to reduce subsequent practice effects across sessions. Subjects will also practice Choice Reaction Task and Precision Force Task, both tasks are described below. The last step in the initial assessment session will be exposing subjects to TMS, beginning with motor threshold determination, followed by an assessment of the targeted functional parietal-motor pathway for the grasp task using a dual-site TMS method described below, and then a 3-min trial run of iTBS to the PPC target. In our experience, ~10-15% of subjects cannot tolerate iTBS, so this will eliminate those subjects without having wasted an expensive fMRI session.

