- **Choice Reaction Time:** The choice reaction time (cRT) is a simple visuomotor task that will be used to control for visuomotor reaction times. We will use a 2-choice version of the cRT to assess the effect of simple visuomotor learned associations on visuomotor reaction time. For the task, a "1" or a "2" will appear on a computer screen ~80 cm in front of the participant and the participant will have to press the corresponding key on the keyboard as fast as they can. The probability of appearance of each number is set to 50%. Each task consists of 40 trials. Performance time will be calculated by the mean reaction time on correct trials at each time point. Participants will complete this task following each 9-HPT session. The participant will complete the cRT three times during each session.

**See below for primary outcome 1, secondary outcomes 1, 7, 8, 9 & 10.*

Figure 3. Precision Force-Tracking Task. Participants will use a grip-force sensor to keep a cursor within a target circle that moves up and down the screen. In dual-task blocks, participants will need to simultaneously count the number of times the target flashes white.

Surveys for the current study are:

- **Pre-screening:** Participants will be screened for preliminary eligibility prior to scheduling their first study session.
- **Enrollment screening:** Participants will again be screened to confirm eligibility prior to enrollment.
- **Daily screening:** Participants will be screened for eligibility prior to any NIBS administration to confirm enrollment.
- **Exit survey:** Participants will be asked to rate their comfort and experience upon completion of each study session.

NIBS interventions for the current study are:

- **Intermittent Theta Burst Stimulation (iTBS):** A MagPro X100 magnetic stimulator with a 90mm figure-8 coil (MC-B70, MagVenture Inc.) will be utilized to deliver brain stimulation. All participants will receive five consecutive days of stimulation within a two-week period. The 3-minute session of intermittent Theta Burst Stimulation (iTBS) will consist of 10 bursts of high-frequency stimulation (a 2 s train of 3 biphasic waveform pulses at 50 Hz repeated every 200 ms at 80% AMT) repeated every 10 s for a total of 190 s (600 pulses) to the target area. The target area will be located using BrainSight2 neuronavigation system. The baseline structural scan obtained during the scan 1 will be utilized for this localization process.

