To minimize risk: The first step will be slight coil rotations (< 10 degrees), which often reduce stimulation-related pain. If this does not work, the coil will be moved slightly or the stimulation magnitude will be turned down.

2. Headache or neck pain (common, not serious): Headache and neck pain, typically lasting up to a few hours on the day of stimulation, are the most frequent side effects of TMS.

To minimize risk: These side effects are usually managed well with standard analgesics (e.g., single doses of aspirin, acetaminophen, or ibuprofen). Subjects will be instructed to contact the investigators if the headache persists on the following day.

3. Sound exposure (rare, serious): When producing a magnetic pulse train, the stimulating coil produces a series of brief clicks. No evidence of hearing loss has been found in humans exposed to TMS, despite extensive exposure to repeated stimulations over several years.

To minimize risk: Earplugs will be used in this study in all subjects as a precautionary measure.

4. Risk of Seizure Induction (rare, serious): The major safety concern about TMS is the possibility of eliciting a seizure, although TMS has rarely been associated with the induction of seizure, even in patients with epilepsy. For example, a recent international consensus conference rated the risk of seizure inductions during low-frequency rTMS as “rare, and usually protective.” In theory, medications that lower seizure threshold could present an added risk, but we believe this risk is no more than a minimal one in our protocol.

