Record time and duration of seizure.

Do not: restrict movement, insert of force objects into the mouth.

After the seizure: Maintain a clear airway: Subject to rest on his/her side to prevent aspiration. Help to reorient the subject: provide reassurance. Remain with the subject 1:1 until fully oriented and stable. Check vital signs. Have the subject transported to the Emergency Department for assessment.

Documentation: When the subject is stabilized, document the following: Incident preceding the seizure (stimulation parameters, duration of stimulation). Description of seizure (parts of the body involved in the seizure, types of movement, time and duration of seizure). Medical personnel notified and time. Treatment given or emergency measures taken. Any injury incurred during the seizure. Subject's clinical status post-seizure.

5. Light headedness and/or Syncope (rare, not serious): In the setting of altered sensory stimulation, subjects occasionally experience brief loss of consciousness, usually attributable to vasovagal syncopy.

To minimize this risk: Participants are encouraged to be well-hydrated in advance of the sessions. During breaks and upon completion of the protocol, we will ask that subjects rise slowly from the chair and we will monitor them for any signs of fading consciousness.

6. Risks from magnetic or induced stimulation (very rare, serious).

To minimize risk: Although the risk of adverse events due to magnetic fields or induced electrical currents acting on tissue at the parameters proposed in this experiment is virtually non-existent, there is some risk due to these currents interacting with metals or implanted devices in a potential subject. Therefore, rigorous screening procedures will occur to minimize this risk to acceptable levels.

7. For women of child-bearing potential: It is unknown if TMS can pose a risk to fetuses.

To minimize this risk: Participants are asked during their screening whether they are pregnant or are trying to become pregnant, and are not enrolled in the study if they are. Sexually-active women of child-bearing potential will be asked to use a reliable birth control method for the duration of this study.

Participants are asked about their experience at the conclusion of each visit; if they report symptoms, they are asked to rate them (see TMS exit survey in section 29)

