Adverse events and withdrawals from the study will be documented for reporting during dissemination of research activities. Adverse events will be reviewed by [name] to

determine their association with study protocol and assess any changes to the protocol that may be required. Study coordinator and/or PI will submit all reportable events to the IRB according to the reporting timetable.

Risks associated with fMRI:

1. Risk of hearing damage due to noise from the scanner (common).

To minimize this risk, participants will be given foam earplugs to prevent against hearing damage and reduce discomfort due to the loud noises of the MRI scanner.

2. There is a minor risk of discomfort or anxiety from being in the confined space of the MRI scanner (infrequent).

To minimize this risk we will provide the participant with pads and blankets for comfort as well as a two way intercom and an emergency squeeze ball so the participant can inform the fMRI technician they want to end the scan.

3. Sometimes participants report a temporary feeling of lightheadedness, slight dizziness, or nausea after the scanning session. (infrequent)

To minimize this risk, participants will be told to inform the scanning technician as soon as this occurs so they can be helped up from the scanner.

4. Certain scanning protocols have the potential to cause peripheral nerve stimulation which is a light tingling sensation on the skin for a few seconds. It may cause minor discomfort but is not harmful. (Rare)

To minimize this risk, the MRI machine is operated within FDA guidelines so the potential for inducing PNS is low.

5. Risk that the magnetic resonance image will reveal a minor or significant lesion in the brain (e. g. a tumor), previously unknown to the subject, and requiring additional follow-up. (Rare)

In the event of anomalous finding on MRI, the PI would contact the participant and advise them to speak to their healthcare provider about obtaining a clinical MRI scan. Many such abnormalities are not clinically significant, but they may need or want to investigate them further. Participants are advised that scan images will not be routinely examined by a specialist trained to make medical diagnoses. Any abnormalities that a participant may currently have may not be noticed in the images obtained in this experiment and that if they have any current health concerns, they should consult their doctor.

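### Symptoms that start after a stimulation visit and clear the same day fall outside every described collection route, so reported adverse event incidence may be understated by an unknown amount

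*Combined protocol and SAP*

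**What the plan says.** The combined protocol and SAP describes three points at which a symptom could come to light.

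- **Exit survey.** The list of surveys under MEASUREMENTS says "Participants will be asked to rate their comfort and experience upon completion of each study session". The TMS risk section of the APPENDIX adds "Participants are asked about their experience at the conclusion of each visit; if they report symptoms, they are asked to rate them".
- **Participant-initiated contact.** Under the headache and neck pain risk, the APPENDIX says "Headache and neck pain, typically lasting up to a few hours on the day of stimulation, are the most frequent side effects of TMS". The only instruction for the period after the visit is "Subjects will be instructed to contact the investigators if the headache persists on the following day".
- **Pre-session screen.** SUBJECTS and SCREENING has participants screened at enrolment and "prior to all subsequent sessions with questions that include the Transcranial Magnetic Stimulation Adult Safety Screen form". The subjects and screening paragraph of RESEARCH DESIGN lists what the form is meant to exclude, "such as: a previous adverse reaction to TMS" among others. The surveys list gives the purpose of the daily screen: "Participants will be screened for eligibility prior to any NIBS administration to confirm enrollment".

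On use of the data, the APPENDIX says "Adverse events and withdrawals from the study will be documented for reporting during dissemination of research activities". It also says that events will be reviewed for association with the protocol and for any protocol change needed.

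The visit schedule in RESEARCH DESIGN gives about 30 minutes for each of Sessions 3, 4 and 5, about 3 hours for Session 6 and about 1 hour for Session 7. These are the five stimulation visits. The next assessment comes about 7 to 15 days after stimulation.

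**The concern.** The active symptom question comes at the end of the visit, and at three of the five stimulation visits that is soon after iTBS. The protocol's own account of its commonest side effects extends over hours. What happens between exit and the next morning has no assigned collection route unless a headache is still present the following day. Neck pain is not mentioned in the contact instruction at all.

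At stake is the descriptive safety record: how often symptoms occur over five iTBS sessions, how long they last, how severe they become, and whether they worsen with repetition. The protocol commits to reporting this record and to using it to decide on protocol changes.

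**Working it through.** **1. Routes set against types of event**

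| Event after iTBS | Exit survey | Next-day contact | Pre-session screen |
|---|---|---|---|
| Starts before exit, clears the same day | Recorded and rated once; later peak and duration not recorded | No | Eligibility check only; no recall period or rating stated |
| Starts after exit, clears the same day | No | No | As above |
| Headache still present next day | Only if already begun at exit | Yes, if the participant calls | As above |
| Neck pain still present next day | Only if already begun at exit | Not covered by the instruction | As above |

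The second row is the gap in incidence. The first row is a loss of duration and severity that needs no assumption about onset.

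**2. Observation window by session**

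iTBS takes 190 s, or 190/60 = 3.2 minutes. In a visit of about 30 minutes, at most 30 − 3.2 = 26.8 minutes can lie between the end of iTBS and exit, less set-up. Session 6 lasts about 180 minutes, six times as long (180/30). How much of that follows iTBS is not stated, although the measures feeding the immediate post-intervention outcomes would have to come after stimulation. At Session 7 the scan begins about 5 minutes after rTMS and is finished within 60 minutes. So the window is not constant over the five sessions.

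**3. Size of the possible understatement**

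The documents state no adverse event rate, onset distribution or capture probability, so there is no figure to reproduce. The following is an illustration on assumed inputs. Let p be the true probability of an event per session, and f the share of events that start after exit and are never reported later. Take sessions as independent and f as constant. Then:

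- observed per-session rate = p(1 − f)
- true share of participants with any event in five sessions = 1 − (1 − p)^5
- observed share = 1 − (1 − p(1 − f))^5

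| p (assumed) | True share | f = 10% | f = 25% | f = 50% | f = 75% |
|---|---|---|---|---|---|
| 5% | 22.6% | 20.6% | 17.4% | 11.9% | 6.1% |
| 10% | 41.0% | 37.6% | 32.3% | 22.6% | 11.9% |
| 20% | 67.2% | 62.9% | 55.6% | 41.0% | 22.6% |
| 30% | 83.2% | 79.3% | 72.0% | 55.6% | 32.3% |
| Observed/true | | 0.91–0.95 | 0.77–0.87 | 0.53–0.67 | 0.27–0.39 |

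The direction is always downward. The size runs from trivial to large depending on f, and the documents give no value for f.

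**4. Effect on a trend across sessions**

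Suppose the true rate is flat at p = 10%, with f = 50% at Sessions 3 to 5, 10% at Session 6 and 25% at Session 7 (all assumed). The observed rates are 10% × 0.50 = 5% three times, then 10% × 0.90 = 9%, then 10% × 0.75 = 7.5%. A flat rate would look like a rise at Session 6 because the visit is longer.

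**The case against.** The strongest reply is that the protocol gives a duration for headache and neck pain, not an onset time. A symptom that begins during the 190 s of iTBS and lasts for hours is still present when a 30-minute visit ends, so long duration makes capture at exit more likely. This stands. A reader might infer from the short visits that the commonest adverse events are largely missed. The documents do not support that: it would need more than about half of events to start after exit and never be reported, and nothing in the text says so. Sessions 6 and 7 also keep participants under observation for longer.

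Second, participants are questioned again before every later session, with a form that looks for a previous adverse reaction to TMS. So the exit survey is not the only time they are asked anything. This stands too, but it does not close the gap. The stated purpose of that screen is eligibility, and no recall period, rating or transfer to adverse event records is described. Nothing shows that a headache the protocol classes as common and not serious would be recorded through a contraindication screen. The form is not reproduced in the public document, so it may hold a suitable question; the protocol does not say that it does.

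Third, a reader might infer that tolerability cannot be compared between arms. That does not follow. All three arms share one visit and survey schedule, and incomplete capture on a common schedule does not rule out a descriptive comparison. Adverse events are not among the 4 primary or 12 secondary outcomes, and no test between arms is planned for them.

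Finally, exit ratings after every session would show some trends. That is correct, but the unequal windows make such a trend hard to interpret.

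**Conclusion.** The point holds as a gap in descriptive safety collection. It rests on the described procedures being the ones followed, with the pre-session screen used as stated, for eligibility. On that reading, three things follow:

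- symptoms that start after exit and clear the same day are not systematically captured;
- duration and later peak are not recorded for symptoms present at exit;
- nothing is scheduled between the last stimulation at Session 7 and the assessment 7 to 15 days later.

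Reported incidence may be too low. The table above shows only how the understatement would depend on an unknown share and is not an estimate for this trial. The efficacy outcomes are untouched. The change is worth making because following the plan exactly as written can understate the events it undertakes to review and report, and the remedy is small.

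**What to change.** Add one look-back item to the existing pre-session screening at Sessions 4 to 9: any symptom since the last visit, with onset, duration, severity on the exit-survey scale, and medication taken. The surveys list ties the daily screen to NIBS administration, so state that the item is also asked at Session 8, which is fMRI only. If Sessions 8 and 9 fall on the same day, ask it once.

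Record positive answers as adverse events. Tabulate events descriptively by randomised arm and by session of stimulation, with exit-survey and look-back reports in separate columns so that the unequal exit windows remain visible. If the current screening form already asks this, the change reduces to saying so, with its recall period and its route into the adverse event record.

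The cost is one item on a form already in use and one table. Reported rates will be somewhat higher than under exit-only collection, and recall for the last stimulation session runs to as much as 15 days. No change to stimulation, schedule or the contact instruction is implied.
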